2.1 Planned Analyses

2.1.1 Mortality Trial

The primary prespecified analysis will use the number of deaths in each community as the outcome variable. For analysis, a death is counted when an individual in the target age range 1–59 months (inclusive) is on census and is not on the next census due to death. Census 0 takes place at the beginning of the study, and each subsequent census takes place approximately six months later. The outcome variable is derived by summing the deaths in each period.

Primary Analysis (Mortality Study).

The primary analysis will be conducted as negative binomial regression. The number of personyears (for persons in the target age range) is derived by summing the person-times for each period. The community-level predictor consists of treatment arm for the community. Specifically, the treatment variable is a community level variable, not an individual level variable. An additional categorical regressor will be included for the country. The likelihood-ratio will be computed, and the statistical significance assessed by permutation testing. Specifically, we will assess the significance of including treatment arm at a two-sided level of 0.05 (a mortality effect in either direction will be statistically significant). The number of permutations is chosen as 10,000, large enough to minimize Monte Carlo error; consecutive runs using a prespecified seed will be reported (and if the Monte Carlo confidence interval for the P-value includes the value 0.05, a new set of 100,000 runs will be conducted and the value reported). An estimated aggregation parameter over 30 will result in the choice of Poisson regression. Evidence of poor fit (based on deviance and/or score residuals) will result in reporting of additional models, beginning with estimation of country-specific aggregation parameters. (Note that the primary analysis remains the single multi-country negative binomial regression, with permutation-based significance testing.)

Individuals who are in the target age range at the beginning of any study period, but who are no longer in the target age range by the end, are considered to be fully enrolled and contribute the full amount of person-time for that period.

All three sites will be aggregated together for the single primary prespecified analysis. The intent is a single negative binomial regression for all three countries together, as the single outcome of the trial.

Model adequacy will always be checked (e.g. overdispersion for count models), and leaveone-out influence plots will be conducted to indentify highly influential single observations. All analyses in this trial will always account for the clustered (community randomized) design.

In the event of an unanticipated rare event (such as a natural disaster or bus accident) in part of an area, sensitivity analysis will be conducted. Analysis omitting this region will be reported, as well as a stratified permutation test in which we compare treatment and control within strata defined by the affected region. While entirely unsuitable for primary analysis, under certain circumstances it may be possible to remove mortality due to the rare event; we would propose reporting this analysis as well.

Secondary Analyses (Mortality study)

All secondary analyses will be sharply distinguished from the primary prespecified analysis and are as the following:

1. Age, treatment group, and country will be used as a covariates in the primary analysis model.

- 2. Negative binomial regression for each time period will be analyzed, using time, country, and treatment.
- 3. A Poisson regression at the individual level comparing treatment groups, using each period of time.
- 4. Negative binomial regression contrasting the first and second years.
- 5. Negative binomial regression using a country-treatment interaction.
- 6. Treatment effect by age will be analyzed using subroups of patients defined by the following age brackets: [1, 6), [6-12), [12-18), [18-24), [24, 60). Age of the child will be the age captured at enrollment.
- 7. We will compare the cause of death, as determined by Verbal Autopsy, between the two arms, using a 2 x k table, permuting by randomization unit.
- 8. Analyses will be conducted for each country, using data from that country only. This analysis will be negative binomial regression with treatment assignment for each village as the covariate.
- 9. An on-treatment analysis of mortality will be restricted to those taking the medication (or placebo) (i.e., comparing placebo-takers to medication-takers).
- 10. Analysis of those censused but too young to treat will be conducted.
- 11. Data will be formatted to include the Phase 24 vital status of all persons found alive at any of the Phases 0, 6, and 12 (with no indication of them dying in the interim) instead of *only considering the vital status of persons alive at phase 18* census.
- 12. Subgroup analysis of children eligible for 4 treatments, but receiving only 1, 2, 3, or 4 treatments by arm (1 vs. 1, 2 vs. 2, 3 vs. 3, and 4 vs. 4 treatments).
- 13. A secondary analysis will be conducted on every child who died and had a treatement (antibiotics or placebo) assessing if:
 - a. The time of death differs between arms (within a year), using a test of equality of circular distributions (using the phase angle as the outcome variable), with a supplementary comparison conducted by fitting negative binomial regression based on linear predictor $A_i \sin (\theta t + \phi)$, where the null hypothesis is that the phase offset ϕ is independent of treatment (similarly, we may compare equality of circular means using a two-sample Edwards test). Note that in this analysis, a test of the equality of the amplitude A_i will also be reported. We will conduct goodness of fit tests using higher order trigonometric terms.
 - b. The time between treatment and death differs between treatment arms will be compared by performing a survival analysis that accounts for country. Note that in order to do a survival analysis, we will include children that survived in the analysis.

- c. The times of treatment (in children that died) between the two arms a Wilcoxon rank sum test comparing the time of treatment in the deceased between the two groups using the Wilcoxon rank sum test.
- 14. Spatial analysis. Secondary analysis will include geographic region as follows. First, we will present a plot of the reduction in mortality by region within country (e.g. zone in Malawi) versus the mortality rate in the placebo communities in that region. This will be done across all countries. Additional data (poverty indices) may be included in such analyses. Such analyses, exploratory in nature, will be sharply distinguished from prespecified outcomes.
- 15. Analyses will be reported using dose (or recorded height/weight as applicable). We will also conduct models in which the number of received treatments is used as a predictor. This is a secondary analysis.
- 16. As stated elsewhere, we will report results of comparing mortality per protocol across arms. We will also report a comparison of people who received treatment (whether placebo or azithromycin) to those who did not. The per-protocol analysis is an important secondary analysis whose results will be highlighted. Comparison of participants to nonparticipants is expected to yield a large effect, but we expect little power for the clinical trial (azithromycin vs placebo) comparison.
- 17. Alternative outcomes will be considered including:
 - a. Verbal autopsy using permanova to test the significance of the treatment variable. Missing verbal autopsy data will not be imputed.
- 18. Subgroup analysis measuring the effect of biannual azithro vs biannual placebo on mortality among subgroups of malnutrition in the MORDOR mortality communities in all countries

2.1.2 Morbidity Trials

Primary Analyses (Morbidity Study).

The morbidity analyses are to be conducted on a country-specific basis. Each outcome will be addressed in a separate analysis. Outcomes are taken at 0, 12, and 24 months.

The outcome and analysis plan for all non-core studies must be submitted to the Steering Committee for approval.

The outcomes for this study are listed on www.clinicaltrials.gov. Analyses may be conducted at the village level (accounting thus for clustering), or, when possible, at the individual level accounting for clustering by using mixed effects regression. The listed primary outcomes (4 February 2015) are:

- 1. Height over time in children aged 1-60 months (Niger & Malawi)
- 2. Weight, corrected for height over time in children aged 1-60 months (Niger & Malawi)
- 3. Fraction of macrolide resistance in nasopharyngeal swabs in children 1-60 months (core). Note that for Niger, this is phenotypic, and is a binary outcome at the individual level.
- 4. Fraction of macrolide resistance from stool specimens in children 1-60 months (core). For Niger, this includes RNA, DNA, and TAC-card methods (a binary outcome at the individual level).
- 5. Fraction of macrolide resistance by nasal swabs in children 1-60 months (Niger only). For Niger, this is based on RNA and DNA sequencing (a binary outcome at the individual level).
- 6. Presence of malaria parasites in children 1-60 months (core activity)
- 7. Fraction of conjunctival swabs yielding ocular chlamydia in children 1-60 months (Niger)

Nonnormality, heteroskedasticity, clustering, and outliers will be assessed appropriately.

Secondary Analyses (Morbiditiy Study).

Common templates will be used. Analysis will use cluster-level variables for malaria parasites, macrolide resistance in NP swabs, macrolide resistance in nasal swabs, macrolide resistance in stool specimens, and ocular chlamydia. Clustered logistic regression using baseline values will be used, with the outcome being the 12 and 24 month observations, and time and treatment as covariates in addition to baseline values. Permutation P-values will be reported.

Model checking will be performed to identify poorly fitting models, using the residuals versus fitted values plot and by finding high leverage points. Significance testing will be conducted using permutation tests.

The analysis will follow these guiding principles: (1) All data from all available participants will be included, regardless of whether the patient contributed data to all time periods, or to only a subset of periods; (2) The analysis must reflect the longitudinal nature of the followup and the clustered nature of the design, (3) Permutation testing will be used to compute the P-value, (4) The model must be fully prespecified prior to any analysis of any kind.

If a village randomized to the morbidity study has fewer than 40 children upon census, an additional morbidity village may be recruited in its place.

All secondary analyses are identified as the following:

- 1. Repeated measures of outcomes for children present at baseline and possibly followed for 24 months. using 0, 12, and 24-month measurements (or all time points processed).
- 2. Analyze additional outcomes: WHO z-values (height for age, weight for height, weight for age) and MUAC. P-value will be adjusted for these additional outcomes.
- 3. Separate outcome using cross-sectional post-test children 25 months and under using 0.05 alpha. Analysis will be similar to longitudinal (height for age, weight for height, outliers, etc. Note that these children were not eligible for the primary analysis.
- 4. Community-level varaiables will be considered from CSI records.
- 5. Per-protocol analysis will be performed by arm, i.e. only including those who took the treatment.
- 6. Other outcomes by treatment arm at 24 months will include percent wasted and percent stunted. Permutation p-values will be computed here.

Sensitivity analysis including the outliers as well as dissociating the measurements in a repeated measures analysis will be conducted. Appropriate consideration will be analyzed for transfromation, heteroskedacity, and outliers. Additional prespecified secondary analyses are listed on www.clinicaltrials.gov.

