1.2 Morbidity Trial

The trial profile is given in the Manual of Operations. In the morbidity trials, communities are randomized to two arms: **AzithroPlus**, or **ControlPlus**. At each study site, 15 communities each are randomized to **AzithroPlus** and to **ControlPlus**. The trial is a placebo controlled, double masked, community randomized, multicenter clinical trial. The profile is given in the Manual of Operations, Ch. 3.

2 Statistical Analysis

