2.1.3.4 Primary MicrobiomeAnalysis

Primary Analysis for rectal swabs collected pre-morbidity study, 16S-sequencing

Pre-Morbidity RCT (a.k.a. "mini-microbiome") will analyze 80 1-60 month old kids, randomized to placebo or azithromycin. We will obtain pre-treatment rectal swabs on day 0 and

post-treatment rectal swabs on day 5. We will compare diversity between arms at day 5, and between time points in each arm. Specific diversity measures to be examined are Shannon's Index (primary), Simpson's Index.

Primary Analysis for rectal swabs collected at 12-months, RNA-sequencing

Primary Analyses for the 12 month rectal swabs will conducted on pooled samples. We will use PERMANOVA on an **L2-norm** distance on bacterial **reads** to determine if treatment significantly explains the difference between the two groups.

Primary Analysis for rectal swabs collected at baseline and at 24 months, RNA and DNA sequencing; individual level analysis, not pooled. We propose to conduct PERMANOVA based on L2-norm; the outcome is the distance in centroid of the whole sequences, comparing the two treatment groups. Primary analysis is posttest only, but we will report comparisons at baseline as well.

PrimaryAnalysis for conjunctiva swabs, RNA-sequencing

Primary Analyses for the 24 month **conjunctiva swabs-RNA sequencing** will conducted on pooled samples. We will use PERMANOVA on an **L2-norm** distance on bacterial **reads** to determine if treatment significantly explains the difference between the two groups.

Primary analysis for rectal swabs at 36-months, DNA-sequencing

Primary analysis on the rectal swabs will be conducted on pooled samples. We will be using DESeq2 to determine if Campylobacter upsaliensis is upregulated in the placebo arm compared to the azithromycin arm. LEfSe will be used as a sensitivity test.

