3.2 Morbidity Trial

Assuming approximately 12% baseline resistance (based on previous studies) and an ICC of approximately 0.051 (derived from the TEF study), we anticipate approximately 80% power to detect a difference of 18% (i.e., comparing 12% to 30%) assuming 80% carriage of pneumococcus and 10 specimens per community. For resistome comparisons, we anticipate approximately 80% power to detect a 16% difference (comparing 12% to 28%). We anticipate five such comparisons: (1) nasopharyngeal DNA, (2) nasopharyngeal RNA, (3) rectal DNA sequencing, (4) rectal RNA sequencing, and (5) rectal TAC-card.

4 Randomization

Simple random sampling will be used in each country. Within each country, a full list of eligible communities will be provided, and used to fill a column of a table. A second column will be populated with treatment arm names as follows. First, fifteen rows will be filled with the name **AzithroPlus**, and fifteen with the name **ControlPlus**. Then, one half of the remaining rows (rounding to even) will be filled with the name **Azithro**, and the remaining filled with the name **Control**. This column will be shuffled at random, yielding an assignment for each community.

Note that there is no stratification other than country, and the morbidity communities are randomized from the same pool as the mortality communities.

The randomization will be conducted using R. The function sample with option replace=FALSE will be used to conduct the random shuffling. Note that the choice of the random number seed completely determines the randomization. To ensure the integrity of the randomization, we will choose the seed as follows. We will use the units (least significant digit) of the daily high Fahrenheit temperature in eleven selected US cities on 15 July 2013 as reported by the National Weather Service. A confidential ordered list of these cities will be provided to the DSMC.

Masking will be strictly enforced. Each study site will provide one individual to whom the randomization list will be provided. Investigators and field teams must remain masked and must make no effort to determine which arm a community has been randomized to within the mortality trial or within the morbidity trial.

5 Abbreviations

ANCOVA Analysis of covariance

DSMC Data and Safety Monitoring Committee

HAZ height for age Z score

MUAC Mid upper arm circumference

SAP Statistical Analysis Plan

TF Trachomatous inflammation—follicular

TI Trachomatous inflammation-intense

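### SAP 2.1.2 names no baseline covariate for the primary analyses of morbidity outcomes 3–7, while the baseline-adjusted model for these outcomes sits under the Secondary heading

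*SAP*

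**What the plan says.** SAP 2.1.2, Primary Analyses (Morbidity Study), states that "Outcomes are taken at 0, 12, and 24 months" and then that "Analyses may be conducted at the village level (accounting thus for clustering), or, when possible, at the individual level", the latter with mixed effects regression to allow for clustering. It lists seven primary outcomes. Items 3–7 are macrolide resistance in nasopharyngeal, stool and nasal samples, malaria parasites, and ocular chlamydia. No baseline covariate is named for any of them.

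Under Secondary Analyses, the same section turns to these five outcomes: "Clustered logistic regression using baseline values will be used, with the outcome being the 12 and 24 month observations". Time, treatment and baseline values are the covariates, and permutation P-values are reported. The guiding principles that follow require an analysis that reflects the longitudinal follow-up and a model that is fully prespecified before any analysis.

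Protocol 5.2.1 plans blood, nasopharyngeal and stool or rectal samples on 40 children per community at baseline, 12 and 24 months. Nasal and conjunctival swabs are non-core (Protocol 5.2.2), and sites that take them may do so at the same visits. Protocol 3.1 draws a simple random sample of children at each of these visits. SAP section 4 states that allocation is not stratified other than by country.

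**The concern.** Each country's morbidity comparison is small: "15 communities each are randomized to" each arm. With simple allocation, the arms can differ at month 0 by chance. At 12% prevalence and an ICC of 0.051, the between-arm difference in mean baseline prevalence has a standard deviation of √(2 × 0.12 × 0.88 × DE / (15m)), where DE = 1 + (m − 1) × 0.051. That is about 4.9 percentage points with m = 8 isolates per village and 3.4 with m = 32. An unadjusted primary analysis carries part of that difference into the treatment contrast, in proportion to how strongly village levels persist.

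The SAP already contains a model that would remove this part, but does not say that it is the primary one. At stake are some power and a definite primary model. Type I error is not at stake: a post-treatment comparison of randomized arms is valid.

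**Working it through.** **Inputs.** There are 15 communities per arm (SAP 1.2). SAP 3.2 gives "Assuming approximately 12% baseline resistance (based on previous studies) and an ICC of approximately 0.051" and states "80% power to detect a difference of 18% (i.e., comparing 12% to 30%) assuming 80% carriage of pneumococcus and 10 specimens per community", which is about 8 isolates per community. For the resistome it gives about 80% power for 12% against 28%. Two-sided alpha of 0.05 is stated for the morbidity primaries only in the contingency-study SAP, which follows the Stage 1 template, and is assumed here. The baseline-to-follow-up correlation is not given and is varied.

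**Step 1: reproduce the stated power.** Effective n per arm = 15m / DE.
- Nasopharyngeal: DE for 10 specimens = 1 + 9 × 0.051 = 1.459, and 15 × 8 / 1.459 = 82.2. SE = √[(0.12 × 0.88 + 0.30 × 0.70) / 82.2] = 0.062, and 0.18 / 0.062 = 2.9. Power is 80.1% (t, 28 df) or 81.5% (pooled z). With DE computed on 8 isolates (1.357, effective n 88.4) it is 82.9% and 84.2%.
- Resistome, 10 specimens: 150 / 1.459 = 102.8. Power is 80.7% (t) or 82.3% (pooled z).

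The stated 80% is reproduced.

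**Step 2: gain from adjustment at a given correlation r.** Adjustment multiplies the residual variance by (1 − r²). From 80% power the noncentrality is 2.80, so power = Φ(2.80 / √(1 − r²) − 1.96). The t column starts from 80% on 28 df and loses one df.

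| r | z | t, 27 df |
|---|---|---|
| 0.2 | 81.6% | 81.5% |
| 0.3 | 83.6% | 83.5% |
| 0.35 | 84.9% | 84.8% |
| 0.4 | 86.4% | 86.3% |
| 0.5 | 89.9% | 89.8% |

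**Step 3: what r the SAP's inputs allow.** With a fresh random sample at each visit, r = s × √(rel₀ × rel₁). Here rel = m × ICC / DE, and s is the correlation of true village prevalence between visits.
- 8 isolates at both visits: rel = 0.408 / 1.357 = 0.30, so r is at most 0.30 (s = 1), and 0.18–0.24 for s = 0.6–0.8.
- 10 at both visits: rel = 0.510 / 1.459 = 0.35, so r is at most 0.35, and 0.21–0.28 for s = 0.6–0.8.
- All 40 children at baseline (32 isolates, or 40 specimens) against 8 or 10 at follow-up: r is at most 0.44 or 0.49, and 0.35 or 0.39 at s = 0.8.
- 32 isolates at both visits: r can reach 0.63. DE is then 2.581, effective n is 186, and unadjusted power for 12% against 30% is already about 99%.

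With 8–10 specimens per visit, r = 0.4–0.5 would need an ICC of r / [m − (m − 1)r]: 0.077–0.111 for m = 8, or 0.062–0.091 for m = 10. Both ranges lie above 0.051.

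**Step 4: simulation.** Beta-binomial villages, t-test against ANCOVA on village proportions at one follow-up visit, 6,000 runs each (Monte Carlo standard error about 0.5 points per figure).

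| Baseline / follow-up specimens | s | Unadjusted | Adjusted |
|---|---|---|---|
| 8 / 8 | 1 | 82.4% | 84.3% |
| 8 / 8 | 0.7 | 83.2% | 83.6% |
| 10 / 10 | 1 | 80.4% | 84.2% |
| 10 / 10 | 0.7 | 80.8% | 80.8% |
| 32 / 8 | 1 | 82.5% | 88.2% |
| 40 / 10 | 1 | 80.3% | 88.7% |

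**The case against.** The strongest reply is that the adjusted model is the common template for these outcomes and only happens to stand below the Secondary heading. The SAP introduces it as a common template and later lists six numbered secondary analyses, and the adjusted model is not among them. This is a fair reading, but it shows only that the designation is ambiguous. The paragraph that carries the Primary label still leaves the model open, against the SAP's own rule of full prespecification.

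The second reply is that the gain is small, and this stands. With r at most 0.30–0.35, baseline explains at most 9–12% of the village-level variance (0.30² to 0.35²); most of the rest is sampling noise within villages.

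Two stronger readings are tempting, and the documents support neither. First, because month 0 is listed among the outcome times, a reader might infer that it will be averaged into the treatment contrast and dilute the effect. No section specifies such a model. The sentence reads as a collection schedule, and the one model written out uses months 12 and 24 as outcome. Month 0 may also enter legitimately as an outcome in a longitudinal model that constrains the arms to equal baseline means. Second, SAP 2.1.3.4 says of the baseline and 24-month rectal sequencing that "Primary analysis is posttest only, but we will report comparisons at baseline as well". A reader might carry the power gain over to it. The gain above is for a single village proportion. It does not transfer to a multivariate distance test, for which the SAP states no power.

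**Conclusion.** The point holds as a modest, nearly free improvement. The primary analyses of items 3–7 name no baseline covariate, and the model that uses baseline is not designated primary. For resistance, at the SAP's own ICC and specimen numbers, the supportable gain is about 0 to 5 power points. The upper end assumes 10 usable specimens at both visits and perfectly stable village prevalence; with stability of 0.7 the simulated gain is close to zero. Gains of roughly 6 to 8 points need the baseline to use all 40 children, only 8–10 specimens at follow-up, and highly stable village levels. If all 40 are tested at both visits, power for the planned difference is already near its ceiling, so adjustment would help only for smaller differences.

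These figures rest on two-sided alpha of 0.05, a single follow-up visit, fresh samples at each visit, and a correlation that the documents do not supply. SAP 3.2 gives no ICC or power for malaria or chlamydia, so their gain could be larger or smaller and cannot be stated.

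**What to change.** In SAP 2.1.2, name the baseline-adjusted model as the primary analysis for items 3–7. The outcome is the 12- and 24-month observations. The covariates are community month-0 prevalence, time and treatment. The P-value comes from permuting treatment across communities. State that month-0 prevalence is computed from all children tested at baseline, even where fewer specimens are processed at follow-up. Keep the unadjusted analysis as a sensitivity analysis. Enter the change in the SAP's revision history before the morbidity outcomes are compared by arm, in line with its prespecification rule. No change to the rectal PERMANOVA follows from this point.

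The cost is wording and about one of 28 degrees of freedom. The model is already written, and the core baseline samples are already planned. For nasal and conjunctival swabs, the covariate is available only where the site takes them at month 0.

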4.1. Eligible Communities

To be eligible for the trial, a community must meet the following criteria:

- 1. The community location in target district.
- 2. The community leader consents to participation in the trial (this does not obviate the need for individual consent, but without overall leadership consent, the community as a whole cannot be part of the trial).
- 3. Eligible communities estimated population of between 200–2,000 people.
- 4. The community is not in an urban area.

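### SAP 2.1.2 allows a small morbidity village to be replaced after randomization, but every listed community already has an arm and the swap has no stated source, arm, timing or analysis rule

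*SAP*

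**What the plan says.** The replacement rule is one sentence in SAP 2.1.2 (Morbidity Trials): "If a village randomized to the morbidity study has fewer than 40 children upon census, an additional morbidity village may be recruited in its place".

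SAP section 4 (Randomization) describes the allocation. The frame is complete: "Within each country, a full list of eligible communities will be provided, and used to fill a column of a table". Thirty rows are labelled AzithroPlus or ControlPlus, 15 each. "Then, one half of the remaining rows (rounding to even) will be filled with the name" Azithro, and the others become Control. "This column will be shuffled at random, yielding an assignment for each community". The section adds that "the morbidity communities are randomized from the same pool as the mortality communities", and, on the seed, "Note that the choice of the random number seed completely determines the randomization". Protocol 3.1 agrees that all four arms come from one list per country.

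Three other provisions bear on the point. Protocol Chapter 3 keeps the morbidity communities out of the mortality comparison. Protocol 4.1 sets community size ("Eligible communities estimated population of between" 200 and 2,000 people) and no minimum number of children. Protocol 5.2.1 and 9.1 call for a random sample of 40 children aged 1–60 months per morbidity community.

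**The concern.** The swap rule and the randomization do not fit together. Once the shuffle is done, no eligible listed community is without an arm, so the replacement has to be taken from the mortality trial or from outside the documented allocation. The SAP does not say which, and it leaves open everything else that would keep a swap harmless:

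- how the replacement is chosen, and whether it takes the arm of the village it replaces;
- which census counts. Censuses run every six months to month 24, and a count made after treatment could itself be affected by treatment;
- which children count. The morbidity census covers ages 0–12 years (Protocol 5.2.1), while the sample is of ages 1–60 months;
- whether the replaced village's data are kept, dropped or analysed separately;
- who decides, since the wording is permissive.

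Morbidity analyses are country-specific, with 15 clusters per arm, and SAP 2.1.2 makes permutation testing a guiding principle for the P-values. A permutation test needs a defined set of randomized units and a known allocation scheme. After an undocumented swap, neither is fixed in advance. At stake are the integrity and traceability of the morbidity comparisons; sample size is a lesser matter.

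**Working it through.** **1. Are any listed communities left over?** The list sizes are in SAP 3.1.2 and 3.1.3.

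- Niger: 646 listed − 30 morbidity = 616, all labelled Azithro or Control. Unassigned: 646 − 30 − 616 = 0.
- Tanzania: 644 − 30 = 614. Unassigned: 644 − 30 − 614 = 0.
- Malawi: no final list size is given, but section 4 applies the same procedure in each country.

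The only off-list communities described are the pilot villages (Protocol 11.2), which are non-study villages without an arm.

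**2. Can the trigger be met?** Taking *children* to mean those aged 1–59 months, use the fractions in SAP 3.1.1 to 3.1.3.

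| Country | Fraction | Children in 200 people | People needed for 40 children |
|---|---|---|---|
| Niger | 16.7% | 200 × 0.167 = 33.4 | 40 / 0.167 = 240 |
| Tanzania | 17% | 200 × 0.17 = 34.0 | 40 / 0.17 = 235 |
| Malawi | 19% | 200 × 0.19 = 38.0 | 40 / 0.19 = 211 |

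So an eligible community can fall below 40.

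**3. How often?** The documents give mean sizes but no distribution, so this is an assumption. Take log-normal sizes with the planned means (799, 668 and 600 people), CV 0.4 to 0.8, truncated to 200–2,000. The share below the threshold is then 0.02–0.9% in Malawi, 0.5–5.4% in Niger and 0.9–5.8% in Tanzania. The expected number is below two of 30 villages in each country (30 × 0.058 = 1.7).

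**4. What does keeping a small village cost?** With m children sampled, the variance of a cluster's contribution is proportional to (1 + ICC × (m − 1)) / m. The ICC is 0.051, the SAP 3.2 value for resistance.

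| m | Factor | Against m = 40 |
|---|---|---|
| 40 | (1 + 0.051 × 39) / 40 = 0.0747 | – |
| 33 | (1 + 0.051 × 32) / 33 = 0.0798 | +7% |
| 25 | (1 + 0.051 × 24) / 25 = 0.0890 | +19% |
| 20 | (1 + 0.051 × 19) / 20 = 0.0984 | +32% |

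The SAP 3.2 power statement uses only 10 specimens per community, which any of these villages can supply.

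**5. Morbidity power.** SAP 3.2 states about 80% for 12% against 30%. With 10 × 0.80 = 8 isolates per village, the design effect is 1 + 7 × 0.051 = 1.357 and the effective n per arm is 15 × 8 / 1.357 = 88.4. A two-proportion test then has 84.2% power, in line with the stated figure. Losing one village per arm outright (14 × 8 / 1.357 = 82.5) gives 81.6%.

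**6. Mortality power.** The SAP 3.1 formula with the Niger inputs (λ₀ = 0.02, λ₁ = 0.017, k = 0.51, y = 668 × 0.167 × 1.9 person-years) gives c = 309.5 per arm, against 312 stated. At 1.8 person-years per child, c = 318.0. Using 1.8, power is 78.7% at 308 clusters per arm (616 / 2) and 78.6% at 307. Moving one mortality cluster per arm into the morbidity trial costs about 0.1 percentage point for Niger alone.

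**The case against.** The strongest reply is that a swap need not harm the comparison. Census workers are masked (Protocol 5.1.1), and each household's census is locked before treatment is given (Protocol 6.1). A swap at the first census would therefore rest on a blinded, pre-treatment count. A mortality community already carries a random azithromycin or placebo label from the same shuffle. If it were drawn at random within the same arm and kept its label, the morbidity comparison would stay randomized. A fresh random draw for an off-list community would also serve. All of this stands. A reader might infer that the permutation P-values are invalid, but the documents do not show that. They show that none of these safeguards is required.

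A reader might also see a contradiction with the guiding principle that all data from all available participants be included. That sentence goes on to speak of participants who contribute to only some time periods, so it concerns incomplete follow-up and does not govern village selection. Nor does every morbidity P-value depend on permutation: the 36-month rectal analysis uses DESeq2, with no permutation test stated.

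It is tempting to read the June 2016 counts as evidence that swaps took place: 622 mortality units in Niger against 616 on the list, and 631 in Tanzania against 614. They do not show this. Moving a mortality community into the morbidity trial would lower the mortality count, and these counts are higher. The documents do not explain the difference, and the unit definitions may differ.

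Two practical objections have some force. Population at eligibility is only an estimate, so a village could have well under 33 children and cost more than 7% in precision. The ICC of 0.051 is for resistance and may not suit malaria or growth. Finally, on the protocol's schedule the 24-month visits ended in 2017, so new wording cannot change what was done. Reporting and the sensitivity analysis are then the useful parts.

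**Conclusion.** The point holds as a gap in protection of the randomized set. SAP 2.1.2 permits a discretionary replacement after randomization. Under the SAP's own procedure, that replacement must be a mortality community removed from the mortality comparison or a community outside the documented allocation. Source, selection, arm, census and analysis set are all unspecified.

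The likely size is modest. Bias is probably small if swaps were masked and made before treatment. The effect on mortality power is about 0.1 percentage point per cluster per arm for Niger alone. The documents report no swap. How often the trigger is met is not stated; the figures of up to about 6% of communities depend on the assumed size distribution and on reading *children* as ages 1–59 months. The conclusion about the rule itself rests on neither assumption.

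**What to change.** Replace the sentence in SAP 2.1.2 with: *If a randomized morbidity village has fewer than 40 eligible children aged 1–60 months, all are sampled and the village stays in its assigned arm.* Record the superseded rule in the revisions history, so that any swap made under it can be traced.

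Report every village already replaced, with the date, the census that triggered it, the source of the replacement, how it was chosen and its arm. If there were none, say so. Where data exist, analyse the originally randomized set, at least as a sensitivity analysis, with the permutation carried out over that set.

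The cost is SAP wording, a short listing and, if swaps occurred, one further analysis. Small villages contribute less precise estimates (step 4 of the check), but the 10 specimens per community behind the power statement remain available.
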